Johns Hopkins Hospital
[name]
[name]
[contact]
[contact]
Email: [contact]

Study Coordinators

[name], MPH, CCRP
Division of Clinical Pharmacology
[name]
[name]
[contact]
[contact]
Email: [contact]

[name]
Division of Clinical Pharmacology
[name]
[name]
[contact]
[contact]
Email: [contact]

SCHEMA

Rationale	Genvoya, a once-daily single fixed-dose combination tablet for treatment of HIV-infection, consists of two nucleoside reverse transcriptase inhibitors (NRTIs), emtricitabine (FTC) and tenofovir (TFV) alafenamide fumarate (TAF), the integrase strand transfer inhibitor (InSTI) elvitegravir (EVG), and the boosting agent cobicistat (COBI). It is unknown whether Genvoya, taken as a crushed/dissolved tablet, is bioequivalent to when taken as a whole tablet. This is crucial information since a substantial number of HIV-infected individuals suffer from pill aversion that could lead to non-adherence and treatment failure.
Design	Within-subject, fixed-order, two-period, open label study to determine the bioequivalence of oral single dose of whole and crushed/dissolved tablets of Genvoya in healthy adult male and female research participants administered under direct observation.
Population	Up to 20 adult male and female healthy research participants will be enrolled to complete 12.
Intervention	Whole Tablet Period: Single observed oral dose of Genvoya whole tablet Crushed/dissolved Tablet Period: Single observed oral dose of Genvoya crushed/dissolved tablet
Outcome Measures	Primary: To investigate the bioequivalence of oral single whole tablet and crushed/dissolved tablet of Genvoya by characterizing the plasma $AUC_{0-\infty}$ and C_{max} of EVG, COBI, FTA, TAF, and TFV in plasma, after single doses of whole tablet and crushed/dissolved tablet in healthy male and female adult research participants. Secondary: To compare other pharmacokinetic parameters of oral single whole tablet and crushed/dissolved tablet of Genvoya by characterizing the plasma T_{max} and terminal elimination half-life of EVG, COBI, FTA, TAF, and TFV after single doses of whole tablet and crushed/dissolved tablet in healthy male and female adult research participant.
Procedures	Screening: Potential research participants provide written informed consent and undergo evaluation of inclusion and exclusion criteria. Whole Tablet Period (3 days): Research participants will swallow, under direct observation, a single dose of a whole Genvoya tablet, followed by plasma sampling for 72 hours as indicated in Table 1 below. Safety Visit: Participants will return approximately 7 days after the whole-tablet dosing for clinical and laboratory safety assessment visit. Washout: A minimum of 14 will elapse between the two Genvoya doses. Crushed/dissolved Tablet Period (3 days): Research participants will swallow, under direct observation, a single dose of a crushed/dissolved Genvoya tablet, followed by plasma sampling for 72 hours, as indicated in Table 1 below. Final Safety Visit: Participants will return approximately 7 days after the crushed/dissolved-tablet dosing for a final clinical and laboratory safety assessment visit. * Adverse events will be monitored at all study visits and graded using the DAIDS Adverse Events Grading Table (Version 2.1, July 2017) as outlined in the protocol.

Table 1: Pharmacokinetic Sampling Schedule

Sampling Hour	Pre-dose	0.25	0.5	0.75	1.0	1.5	2	3	4	5	6	10	14	24	48	72
EVG	x				x		x	x	x	x	x	x	x	x	x	x
COBI	x		x		x		x	x	x		x	x	x	x	x	
FTC	x		x		x		x	x	x		x	x	x	x	x	x
TAF	x	x	x	x	x	x	x	x	x		x					
TFV	x	x	x	x	x	x	x	x	x		x	x		x	x	x

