A recent study reported the bioavailability results from crushing and splitting the single fixed-dose formulation tablet containing darunavir (DRV), cobicistat (COBI), emtricitabine (FTC), and TAF (7). This was an open-label, randomized, cross-over study in 30 HIV healthy research participants, using a single dose of this fixed dose formulation as whole tablet, crushed/dissolved tablet, and halved tablet. Plasma concentrations for each method of administration were comparable for DRV, FTC, and COBI. Although TAF was bioequivalent for the whole versus split tablet, the crushed/dissolved tablet resulted in 20% reduced TAF AUC. Therefore, further studies are needed to confirm these results. Also, it is crucial to conduct a bioequivalence study with the Genvoya tablet, since this fixed-dose formulation includes EVG, a different ARV class than DRV in the previous bioavailability study (7).

The national treatment guidelines recommend that treatment-naive HIV-infected patients receive an initial combination regimen with InSTI-based therapy (8). Thus, InSTIs are a relevant class of ARV drugs for the treatment of HIV infection, and showing whether these medications can be taken in a crushed/dissolved tablet form can be a lifesaving intervention for individuals who cannot tolerate ingesting a whole tablet formulation.

In this short pharmacokinetic study we will investigate whether an oral single-dose of whole tablets of Genvoya is bioequivalent to a crushed/dissolved form of this medication in healthy research participants.

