4 STUDY DESIGN

The proposed bioequivalence study will have two pharmacokinetic observation periods:

Whole Tablet Period: Research participants will be asked to swallow a single whole Genvoya tablet under direct observation. The first 72-hour pharmacokinetic sampling period for each of the ARV components of Genvoya will occur as outlined in **Table 3**. Participants will return for a safety visit for clinical and laboratory assessments seven days after whole tablet dosing. A minimum 14 day washout period will take place between the whole tablet dosing and the crushed/dissolved tablet dosing.

Crushed/Dissolved Tablet Period: Research participants will be asked to swallow a single crushed/dissolved Genvoya tablet under direct observation. The second and final Genvoya pharmacokinetic sampling will occur as outlined in **Table 3**.

Pharmacokinetic Sampling. Plasma sampling for estimating pharmacokinetic parameters were selected to optimize information content of each sample for each drug (and TFV metabolite of TAF) for robust estimates of T_{max} , C_{max} , $AUC_{0-\infty}$, and terminal elimination half-life. These are based on prior observations of T_{max} and half-life.

Table 3. Pharmacokinetic sampling schedule

Sampling Hour	Pre-dose	0.25	0.5	0.75	1.0	1.5	2	3	4	5	6	10	14	24	48	72
EVG	x				x		x	x	x	x	x	x	x	x	x	x
COBI	x		x		x		x	x	x		x	x	x	x	x	x
FTC	x		x		x		x	x	x		x	x	x	x	x	x
TAF	x	x	x	x	x	x	x	x	x		x					
TFV	x	x	x	x	x	x	x	x	x		x	x		x	x	x

The proposed pharmacokinetic sampling visits will be conducted at the Drug Development Unit (DDU) in the Division of Clinical Pharmacology at the Johns Hopkins Hospital. The DDU staff has extensive experience conducting pharmacokinetic studies in healthy research participants. The DDU will provide study coordinators and other administrative research support, and recruit participants for this study.

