9.2.6 Day 8 (Visits 6 and 11) - Safety Visit

Subjects will return to the DDU 7 days ± 3 days following the direct observed dose of Genvoya for a safety study visit. Subjects will undergo clinical and laboratory evaluations as outlined in the schedule of events. A targeted physical examination is to be driven by any signs or symptoms previously identified that the subject has experienced since the last visit, or newly occurring that the subject has experienced since the previous visit. A targeted physical examination is not necessary if the subject does not have new symptoms. In the absence of new symptoms, a target physical examination may still be required to document resolution of previous findings on physical examination.

Study subjects will be reminded that they must not participate in a conception process. Participants will also be advised regarding HIV prevention during the study.

Adverse events will be monitored throughout the study according to the DAIDS Table for Grading the Severity of Adult and Pediatric Adverse Events. Participants experiencing grade ≥ 3 toxicity that is deemed by the investigator as associated with Genvoya will be discontinued from the study. These subjects will be followed until resolution, return to baseline values, stabilization, or an adequate explanation can be given for their condition. They will complete the last safety evaluation visit outlined in the schedule of events. Patients experiencing grades 1 or 2 toxicity will continue in the study at the discretion of the investigator.

At visit 6, participants will be scheduled to return to the DDU to start the Crushed/Dissolved Tablet Period of the study.

The final safety evaluation visit is also the premature study drug discontinuation visit. They will undergo clinical and laboratory assessments as outlined in the schedule of events.

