13 STATISTICAL CONSIDERATIONS

An equivalence approach with no-effect boundaries of 80 to 125% will be employed, in accordance with the FDA guidance on bioequivalence studies, which define bioequivalence as “the absence of a significant difference in the rate and extent to which the active moiety becomes available at the site of action when administered at the same molar dose under similar conditions (11).

In order to test the primary hypothesis, log-transformed $AUC_{0-\infty}$ and C_{max} after a single dose for crushed/dissolved

Table 4

Confidence Level	Sample Size (N)	Target Distance from Mean to Limits	Actual Distance from Mean to Limits	Standard Deviation (\$)
0.900	5	0.050	0.048	0.050
0.900	13	0.050	0.049	0.100
0.900	27	0.050	0.049	0.150
0.900	46	0.050	0.050	0.200
0.900	70	0.050	0.050	0.250
0.900	3	0.100	0.084	0.050
0.900	5	0.100	0.095	0.100
0.900	9	0.100	0.093	0.150
0.900	13	0.100	0.099	0.200
0.900	19	0.100	0.099	0.250
0.900	3	0.150	0.084	0.050
0.900	4	0.150	0.118	0.100
0.900	5	0.150	0.143	0.150
0.900	7	0.150	0.147	0.200
0.900	10	0.150	0.145	0.250
0.900	3	0.200	0.084	0.050
0.900	3	0.200	0.169	0.100
0.900	4	0.200	0.177	0.150
0.900	5	0.200	0.191	0.200
0.900	7	0.200	0.184	0.250
0.900	2	0.250	0.223	0.050
0.900	3	0.250	0.169	0.100
0.900	4	0.250	0.177	0.150
0.900	4	0.250	0.235	0.200
0.900	5	0.250	0.238	0.250

versus whole tablets will be compared. The adjusted mean differences will be estimated and their 90% confidence intervals calculated. In the case of $AUC_{0-\infty}$ and C_{max} , the estimated differences and confidence limits will be exponentiated in order to compare ratios between tablet forms.

Statistical Methods

The sample size was calculated according to the formulas for a multiplicative model (12). **Table 4** includes sample size calculations for this proposed study (13). If the mean C_{max} ratio or AUC ratio is 1, a sample size of 5 subjects produces a two-sided 90% confidence interval (0.952, 1.048) (i.e., a distance from the mean to the limits that is equal to 0.048, when the estimated standard deviation is 0.050). A sample size of 10 subjects produces a two-sided 90% confidence interval (0.855, 1.145) if the mean C_{max} ratio or AUC ratio is 1, and the estimated standard deviation is 0.25. Assuming a dropout rate of 10%, a sample size of 12 subjects will be required to provide 90% power to demonstrate the bioequivalence of C_{max} with 90% confidence intervals (CI) of 80% and 125%.

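### All participants take the whole tablet first and the crushed tablet second, so the crushed/whole ratio cannot be separated from a period effect

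*Combined protocol and SAP*

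**What the plan says.** The Schema sets out a "Within-subject, fixed-order, two-period, open label study to determine the bioequivalence of oral single dose of whole and crushed/dissolved tablets". Section 4 and the Schedule of Events put the whole tablet in the first period and the crushed/dissolved tablet in the second for every participant. Section 9.2.6 confirms the order: "At visit 6, participants will be scheduled to return to the DDU to start the Crushed/Dissolved Tablet Period of the study". There is no second sequence, replicate period or concurrent control. The documents neither give a reason for the fixed order nor state that period effects are assumed absent.

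Between doses, Section 4 provides that "A minimum 14 day washout period will take place between the whole tablet dosing and the crushed/dissolved tablet dosing".

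For the analysis, Section 13 states that "An equivalence approach with no-effect boundaries of 80 to 125% will be employed", applied to log-transformed AUC and Cmax. It adds that "The adjusted mean differences will be estimated and their 90% confidence intervals calculated", without saying what the adjustment is for.

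Section 1.1 cites an earlier crushed-tablet study of a related fixed-dose combination: "This was an open-label, randomized, cross-over study in 30 HIV healthy research participants". That study found TAF AUC 20% lower with the crushed tablet.

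**The concern.** A within-subject comparison removes differences between people. It does not remove a difference between the first and second occasion. When everyone follows one sequence, any systematic change from period 1 to period 2 goes in full into the crushed/whole ratio, and the 90% confidence interval makes no allowance for it.

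The protocol leaves room for such a change. The light meal in Section 5 has no stated composition and no requirement to match across periods. The washout has a minimum but no maximum. Nothing requires a participant's two sets of samples to be assayed in the same batch.

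The decision is made on limits of 80% to 125%, and the earlier TAF AUC result lies at the lower limit, so a shift of a few percent could change the conclusion in either direction. Section 14.7 says that confirming bioequivalence will give patients the option of crushed tablets. A false claim could therefore affect treatment exposure, and a false failure would withhold that option.

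**Working it through.** **Inputs from the documents.** Limits 0.80 and 1.25, a two-sided 90% interval, and SD 0.25 with N = 10 in the precision statement (Section 13); 12 completers (Schema, Section 6); minimum washout 14 days (Section 4); TFV half-life 32 h (Table 2); 20% lower TAF AUC in the earlier study (Section 1.1).

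**Assumptions.** The documents give no size for a period effect; period-2/period-1 ratios from 0.90 to 1.10 are used for illustration. The SD of the within-subject log ratio is taken as 0.15 to 0.25, which lies within the range of Table 4.

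**Step 1: the plan's own figure.** Half-width = t(0.95, n−1) × SD/√n. For n = 10 and SD 0.25 this is 1.833 × 0.25/√10 = 0.145, which agrees with the plan's statement: "A sample size of 10 subjects produces a two-sided 90% confidence interval (0.855, 1.145"). The precision calculation is thus a paired, single-sequence one with no period term.

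**Step 2: can period be adjusted for?** Take 12 subject columns, one period column and one formulation column, 14 in all.
- Fixed order: rank 13 of 14. The period and formulation columns are identical.
- Six participants in each order: rank 14 of 14. Both effects can be estimated.

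No adjustment of the Section 13 mean difference can therefore remove period under the present design.

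**Step 3: what is estimated.** Expected log difference = ln(formulation ratio) + ln(period ratio). For example, a true ratio of 0.80 with a period ratio of 1.05 is estimated as 0.80 × 1.05 = 0.84.

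**Step 4: effect on the decision.** The table gives the probability that the 90% interval lies within 0.80 to 1.25 (two one-sided t tests, n = 12, 11 df, by numerical integration over the sample variance).

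| True ratio | Period ratio | SD 0.15 | SD 0.20 | SD 0.25 |
|---|---|---|---|---|
| 0.80 | 0.95 | 0.3% | 0.7% | 1.0% |
| 0.80 | 1.00 | 5% | 5% | 5% |
| 0.80 | 1.05 | 28% | 20% | 16% |
| 0.80 | 1.10 | 66% | 46% | 34% |
| 1.00 | 1.00 | 99.8% | 95% | 79% |
| 1.00 | 0.95 | 98% | 87% | 69% |
| 1.00 | 0.90 | 82% | 61% | 45% |

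**Step 5: does carryover prevent reversing the order?** 14 days = 336 h, and 336/32 = 10.5 half-lives of TFV, the slowest analyte. The residual is 0.5^10.5 = 0.07%. It does not.

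**Step 6: cost of two sequences.** With six completers in each order, the period term reduces the error df from 11 to 10, and t(0.95) goes from 1.796 to 1.812, a ratio of 1.009. At SD 0.25 the half-width goes from 0.130 to 0.131 and power at a true ratio of 1 from 78.8% to 78.1%. The error rate at a true ratio of 0.80 stays at 5% whatever the period shift.

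**The case against.** The strongest reply is that nothing in the documents shows that a period effect exists. Both periods take place in the same unit, under direct observation, with the same sampling times and windows. Exclusion 7.2.4 covers medicines in the two weeks before either dose, and Section 8 restricts them during the study. Accrual is staggered over 6–9 months, so season and staff experience are largely not aligned with period. Drift in the assay could be controlled by batching alone.

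The illustration is also selective. It places the true ratio exactly at 0.80, a value taken from one analyte of a different product, among ten primary comparisons (five analytes, AUC and Cmax). A downward shift there makes a false claim less likely, and a larger SD weakens the effect: at an assumed SD of 0.40, upward shifts of 5% and 10% give 7% and 11%.

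The remedy may also cost a little more than stated, because blocking does not guarantee six completers per order. A 7/5 split raises the standard error by 1.4% and an 8/4 split by 6.1%, before the lost degree of freedom.

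Much of this stands. Season, staff familiarity and changing medicines are weak examples, the probabilities are a sensitivity range and not a prediction, and the cost can exceed 0.9%. The main point is untouched. Standardised conduct may make a period effect small, but this trial's data could never show that it had. Pre-dose samples can check carryover, not period.

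**Conclusion.** The concern holds. Formulation and period are completely aliased, and this follows from the design alone, without any assumption. A bioequivalence conclusion would depend on an unstated and untestable assumption that there is no period effect.

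The size of any bias is unknown. The figures in the working depend on the assumed shifts, on 12 completers and on a log-ratio SD of 0.15 to 0.25. Within those assumptions, a shift of 5–10% is enough to change the decision in either direction. This should be corrected before the trial starts, because it affects the primary comparison, cannot be repaired in the analysis, and costs very little to avoid.

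**What to change.** Randomise participants 1:1 to whole-then-crushed or crushed-then-whole, in blocks, aiming for about six completers per order. Analyse log AUC and log Cmax with sequence, period and treatment as fixed effects and subject within sequence as a fixed or random effect. State in Section 13 that this is the adjustment meant. Assay both periods of a participant in the same analytical batch.

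The cost is a change to the protocol and consent wording, a randomisation list, and a pharmacy ready to supply either form in either period. One degree of freedom is lost, plus the small loss of precision noted above if completers are unbalanced. Sample size, visits, washout and blood draws do not change.

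If the fixed order must stay, give the reason, state the no-period-effect assumption, report how the ratios and intervals change over a range of period shifts in both directions, and limit the bioequivalence conclusion accordingly.

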1 INTRODUCTION

1.1 Background

Genvoya, a fixed-dose combination of the two non-nucleosides reverse transcriptase inhibitors (NRTIs) emtricitabine (FTC) and tenofovir (TFV) alafenamide fumarate (TAF), with the integrase strand transfer inhibitor (InSTI) elvitegravir (EVG) and the EVG-boosting agent cobicistat (COBI), is FDA approved for the treatment of HIV-infected patients (1).

Despite the availability of Genvoya, allowing for a single tablet fixed-dose combination and once-daily dosing, a substantial number of individuals living with HIV suffer from pill aversion, dysphagia, odynophagia, or problems swallowing their oral regimens - all of which can contribute to non-adherence (2). These observations are especially important because non-adherence to antiretroviral (ARV) medications is highly prevalent and associated with decreased survival (3). Non-adherence has been estimated at 55% in North American pooled cohorts, and is a vital public health concern, as it leads to treatment failure and transmission of drug-resistant virus (4-6).

Many clinical scenarios make the administration of crushed/dissolved tablets desirable as a potential strategy to overcome pill aversion. However, there is a theoretical concern that the systemic absorption of the active ingredients of tablets may be altered by crushing the pills. In fact, pharmacokinetic and bioequivalence data are lacking for most ARV fixed-dose combinations used in the treatment of HIV-infected patients. It is therefore of substantial practical and clinical interest to know whether ARV combinations such as Genvoya can be taken in crushed/dissolved form with bioequivalence to whole tablet form.

A recent study reported the bioavailability results from crushing and splitting the single fixed-dose formulation tablet containing darunavir (DRV), cobicistat (COBI), emtricitabine (FTC), and TAF (7). This was an open-label, randomized, cross-over study in 30 HIV healthy research participants, using a single dose of this fixed dose formulation as whole tablet, crushed/dissolved tablet, and halved tablet. Plasma concentrations for each method of administration were comparable for DRV, FTC, and COBI. Although TAF was bioequivalent for the whole versus split tablet, the crushed/dissolved tablet resulted in 20% reduced TAF AUC. Therefore, further studies are needed to confirm these results. Also, it is crucial to conduct a bioequivalence study with the Genvoya tablet, since this fixed-dose formulation includes EVG, a different ARV class than DRV in the previous bioavailability study (7).

The national treatment guidelines recommend that treatment-naive HIV-infected patients receive an initial combination regimen with InSTI-based therapy (8). Thus, InSTIs are a relevant class of ARV drugs for the treatment of HIV infection, and showing whether these medications can be taken in a crushed/dissolved tablet form can be a lifesaving intervention for individuals who cannot tolerate ingesting a whole tablet formulation.

In this short pharmacokinetic study we will investigate whether an oral single-dose of whole tablets of Genvoya is bioequivalent to a crushed/dissolved form of this medication in healthy research participants.

1.2 STUDY DRUGS: CLINICAL PHARMACOLOGY AND SAFETY

Genvoya (EVG/COBI/FTC/TAF)

Genvoya is a once-daily single fixed-dose combination tablet for treatment of HIV-infection. One tablet consists of two NRTIs, FTC 200 mg and TAF 10 mg, the InSTI EVG 150 mg, and the EVG-boosting agent COBI 150 mg (1). The FDA recommended dosage of Genvoya in patients ≥ 12 years old is one tablet daily taken with food (1). Genvoya should not be used in patients with a creatinine clearance (CrCl) < 30 mL/min (1). EVG and COBI are highly bound to plasma proteins (1).

Safety. The most common adverse effects with Genvoya are diarrhea, nausea, fatigue, and headaches (1). Most of these adverse events are self-limited and resolve spontaneously. COBI is known to inhibit creatinine secretion that leads to an increase in serum creatinine, and a corresponding reduction in GFR and creatinine clearance although actual GFR is not affected (1). In addition, more patients treated with Genvoya had LDL levels > 190 mg/dL compared to Stribild, 5% and 2%, respectively (1).

Cardiac electrophysiology studies showed that EVG and TAF did not prolong or affect the PR and QT/QTc intervals, respectively, while COBI prolonged the PR interval in one study (1). However, the dose of COBI in the Genvoya tablet is lower than doses evaluated in cardiac electrophysiology study. Therefore, it is unlikely that treatment with Genvoya will lead to clinically important prolongation of the PR interval (1). The effect of the combination regimen Genvoya or FTC on the QT interval is unknown. Genvoya has been giving to healthy research participants in a number of studies with minimal reported toxicity (1). It is also important to underscore that most of the side effects associated with Genvoya occur with chronic use of this ARV medication and, thus, less likely to occur with the short-term term dosing proposed in this bioavailability study.

Genvoya is a category B drug for use during pregnancy (1). No adverse developmental effects were observed in animal studies when the components of Genvoya were administered separately during the period of organogenesis (1). TAF use in women during pregnancy has not been evaluated, while EVG, COBI, and FTC use during pregnancy has been evaluated in a limited number of women (1). Current data showed no birth defects reported for COBI or EVG and no difference in the overall risk of major birth defects for FTC compared with a U.S. reference population (1). It is unknown if COBI, EVG, and TAF are present in human breast milk; FTC has been shown to be present in human breast milk (1).

Clinical Pharmacology. The PK parameters of individual components of Genvoya are listed in **Table 2**. All PK parameter data are taken from the GenvoyaTM package insert for EVG, COBI, FTC, and TAF. Data for TFV, which results from the conversion of TAF, is taken from the VemlidyTM package insert with adjustment of PK parameters for 10 mg dose of TAF in Genvoya vs. 25 mg in Vemlidy, assuming dose proportionality (C_{max} , $AUC_{0-\infty}$, and C_{trough}) and the Genvoya package insert (TFV half-life only which differs significantly from TFV half-life when administered as TDF).

Table 2. Summary of Genvoya constituent drugs pharmacokinetic parameters after oral administration in HIV-infected adults. Mean (SD).

Parameter	Units	EVG	COBI	FTC	TAF	TFV (from TAF)
Dose	mg	150	150	200	10	NA
C_{max}	mg/mL	1.7 (0.4)	1.1 (0.4)	1.9 (0.5)	0.16 (0.08)	0.012
AUC_{0-∞}	mg/hr/mL	23.0 (7.5)	8.3 (3.8)	12.7 (4.5)	0.21 (0.15)	0.16
C_{trough}	mg/mL	0.45 (0.26)	0.05 (0.13)	0.14 (0.25)	NA	0.04
Half-life	hours	12.9	3.5	10	0.51	32

COBI and EVG are metabolized by CYP3A4 enzyme; therefore, concomitant use of these two drugs with CYP3A4 inhibitors could substantially increase their plasma concentration (1). COBI is also metabolized by CYP2D6. CYP3A4 inducers on the other hand, lower COBI and EVG plasma concentrations which may lead to loss of therapeutic effect of Genvoya and development of treatment failure and viral resistance (1). COBI is also an inhibitor of CYP3A4 and CYP2D6 in addition to drug transporters such as breast cancer resistance protein (BCRP), p-glycoprotein (P-gp), and organic anion transporting peptide (OATP) 1B1 and 1B3 (1). Therefore, co-administration of Genvoya with CYP3A4, CYP2D6, P-gp, BCRP, OATP1B1 or OATP1B3 substrates can significantly increase their plasma concentrations.

EVG, a CYP2C9 inducer, can lower plasma concentrations of substrates metabolized through this pathway (1). TAF is a weak inhibitor of CYP3A *in vitro* but not an inhibitor or inducer of CYP3A *in vivo*; TAF is also a substrate of P-gp, BCRP, OATP1B1 and OATP1B3 (1). Therefore, inhibitors of these drug transporters may increase the absorption of TAF. Conversely, drugs that induce the activity of these drug transporters could lead to a reduction TAF absorption and decrease TAF plasma concentrations (1). FTC is renally eliminated and does not undergo biotransformation through the cytochrome P450 pathway (1). Coadministration of Genvoya with drugs that can affect renal function can lead to a reduction of renal elimination of FTC and consequently an increase in FTC concentrations and potential adverse events. Other mechanism of drug interactions with the components of Genvoya besides drug transporters and hepatic drug metabolizing enzymes, include diminished absorption when EVG is coadministered with drugs containing polyvalent cations (e.g., Mg, Al, Fe, or Ca; 1).

